# **Part II: Study Description**

# Randomized Trial of Rosuvastatin for Acutely Injured Lungs from Sepsis

SAILS: Statins for Acutely Injured Lungs from Sepsis

# 1. Background

#### 1.1. Introduction

Pneumonia and extrapulmonary sepsis account for 50-65% of all ALI cases and mortality is high. Over the past decade, several observational studies have reported that patients admitted for treatment of infection and/or sepsis and who were taking a statin as an outpatient have significantly lower mortality and morbidity than patients not receiving a statin. These findings are especially notable because the patients who had received statins had more comorbid conditions such as hypertension, diabetes, coronary artery disease, COPD, renal dysfunction and stroke.

#### 1.2. Observational Trials of Statins in Sepsis and ALI /ARDS

Almog et al. prospectively examined the outcomes of patients with sepsis who had received statins for at least one month prior to admission. Despite the statin therapy group having a higher baseline incidence of hypertension, ischemic heart disease, diabetes, and a trend toward more congestive heart failure, patients on statins were less likely to progress to severe sepsis and end-organ dysfunction. The risk of developing severe sepsis was lower by 16.6% (19 to 2.4%, p=0.001) (relative risk reduction of 87%). Furthermore, the relative risk of death was 0.43 (8.6 to 3.7%, p=0.14). Sixty percent of those developing severe sepsis had 2 or 3 organ failures and one third developed 4-organ failure. Of the 55 patients who developed severe sepsis, only 2 were in the statin group (personal communication, [name]). Unlike most reported observational studies with statins in this population, statin therapy was continued after admission in 75% of patients (personal communication [name]). The Irish Critical Care Trials Group reported that patients on statins with ALI had a trend toward reduced mortality (33.5% to 20.8%). Both publications did not report any toxicity attributable to statins.

In a retrospective study of 388 hospitalized patients with bacteremia, 35 had been taking statins and 353 had not. Mortality was lower in those taking statins (6% vs. 28%, p=0.002). Attributable mortality from bacteremic sepsis was 20% in patients who had not been taking statins and 3% for those who had been taking statins (p=0.01). The reduction in mortality remained significant after multivariate analysis with an odds ratio of 7.6 (CI: 1.01-57.5). Patients on statins were more likely to have diabetes, hypertension, and coronary artery disease.

No patients in the statin group developed a nosocomial bacteremia vs. 27% in the group not receiving statins. No toxicity related to statin use was reported.

Kruger et al. recently published a retrospective analysis of patients admitted with sepsis. Sixtysix of 438 patients were on statin therapy at the time of hospital admission. The patients on outpatient statin therapy were more likely to have diabetes, hypertension, and congestive heart failure and were less likely to be immunosuppressed. All cause mortality was higher in the nonstatin group (23.1% vs.10.6%; p = 0.022). Mortality specifically attributable to bacteremia was lower in statin users (6.1% v 18.3%, p=0.014). Fifty-six of 66 patients in the statin group were continued on statin therapy during the hospitalization and had an all cause mortality of 1.8% as opposed to 23.1% for never-statin users (p=0.0002). Mortality attributable to bacteremia was also reduced (1.8% vs. 18.3%; p=0.0018) and no toxicity from statins was reported.

Hackam et al. evaluated the incidence of sepsis in patients over 65 years of age surviving at least 3 months after hospitalization for an acute coronary syndrome, ischemic stroke or revascularization. Of 141,487 patients, 46,662 were discharged on statin therapy. Using propensity matching, two comparable cohorts were identified (34,584 patients on statin therapy and 34,584 not on statin therapy). The incidence of sepsis during follow up was 71.2 vs. 88.0 per 10,000 patient-years (hazard ratio of 0.81; 95% CI 0.72-0.91).

Thomsen at al. retrospectively evaluated outcomes in nearly 30,000 Danish patients hospitalized for pneumonia, of which 4.6% were taking statins prior to admission. The mortality rate ratios were significantly lower in statin users at 30days and 90days (0.69 and 0.75 respectively). In a prospective observational study by Chalmers et al. of 1007 patients admitted with community acquired pneumonia, statin users had a reduced 30 day mortality (adjusted OR 0.46, 95%CI 0.25-0.85, p=0.01) and reduced incidence of complicated pneumonia (adjusted OR 0.44, 95%CI 0.25-0.79, p=0.006). However, there was no reduction in application of mechanical ventilation or inotropic support. The statin group had reduced CRP values on admission (medians 119 vs. 182, p<0.0001).

Donnino et al. reviewed outcomes in patients admitted through the emergency department (ED) for suspected infection. Twenty three percent of 2036 patients had a statin administered after ED admission. Despite greater comorbidities in the patients receiving statins, mortality was lower by 73%. The investigators have begun an RCT to evaluate statins for patients admitted with suspected sepsis. Schmidt reported reduced mortality in patients with multiple organ dysfunction between statin users versus non-statin users (28 day mortality 33% vs. 53%, p=0.03 and hospital mortality 72% vs. 35% p<0.0001). Donnino and Schmidt did not report any toxicity attributable to statins.

Taken together, these published observational studies show an association between statins and improved outcome in patients with sepsis and bacteremia with no reported toxicity. However, it is not clear if this association is causal or explained by other factors such as better access to healthcare for patients receiving statins. This is in part addressed by a study of Shah et al. examining a cohort from Kaiser-Permanente health care system where all patients have access to health care within the Kaiser system. Patients admitted with a diagnosis of sepsis, SIRS, septic

shock or ARDS were separated into three groups; current statin users, remote users (history of statin usage but not within 2 months before admission) and nonusers (no statin usage in the 12 months preceding hospitalization). Over 23,000 patients aged > 50 years were identified. After adjusting for age and gender only, the mortality hazard ratios were lower in current users than non users (0.78) and, after adjustment for differences in co-morbidities and Charlson scores, current users had lower mortality hazard ratios than remote users and non users (0.80 and 0.85 respectively). Statin users had significantly reduced mortality hazard ratios in comparison to remote and nonusers. Shah et al. have also shown that the mortality benefit observed in the statin users was greater in those on higher statin doses, suggesting a dose response.

#### 1.3. Randomized Trials of Statins for Sepsis

Two prospective RCTs involving the acute use of statins in patients with sepsis who were not on statins prior to hospitalization have been presented but have not yet been published except in abstract form. These two trials are summarized below.

Choi et al. studied atorvastatin (10 mg daily) in 67 patients with sepsis and pneumonia. Baseline APACHE III score, acute lung injury score, pneumonia severity index, and SOFA score at admission, ICU stay and hospital stay were not different between groups. Day 1 cholesterol values were not different between two groups, but Day 7 cholesterol was lower in statin group (92 mg/dl vs. 115 mg/dl, p=0.044). Hospital mortality was reduced in the atorvastatin group as compared to placebo (27.3% vs. 55.9; p=0.026). No adverse events were attributed to atorvastatin.

Montoya et al. conducted an RCT of 80 mg/day simvastatin or placebo for 14 days in 40 patients with sepsis. Simvastatin decreased CRP and an increased Anti-thrombin III. While a shorter length of stay was seen, no differences in survival were noted.

#### 1.4. Negative Observational Trials and Clinical Equipoise

Published observational studies are not unanimous in demonstrating an association between statins and better outcomes, thus supporting equipoise for a randomized controlled trial. Yang et al. found no benefit of prior statin therapy in an Asian population with sepsis and at least one positive blood culture. They analyzed 454 of 763 patients with sepsis and stratified the population between those on statins (>30 days prior to admission) who were continued on statins and those never on statins. There were 104 patients in the statin group (22.9%). Thirty day mortality was not different between groups (19.2% vs. 18.9%, respectively). The authors note that there was no evidence for toxicity from statins. Short term mortality was also not reduced in a study by Thomsen et al. Mortality for hospitalized patients with bacteremia at 30 days was similar (20.0% vs. 21.6%, statin users and non-users). However mortality rates between days 31-180 were reduced in statin users (8.4% vs. 17.5%, adjusted mortality rate ratio 0.44; CI 0.24-0.80).

In a retrospective study of patients with ALI, Kor et al. found that statins did not confer a survival benefit or reduce organ dysfunction. There was a reduction in ICU length of stay, but this may have been attributable to lower disease severity in the statin group as SOFA scores were lower. Fernandez et al. analyzed 438 ICU patients receiving mechanical ventilation for more

than four days, 38 of whom received statins before and during their ICU stay. Statin treated patients were older (72 vs. 62 years) and had higher APACHE II scores (21 vs. 17) and higher hospital mortality (61% vs. 42%). Higher mortality persisted after adjustment for APACHE II predicted risk. The authors concluded that statin use was a marker of higher disease severity, older age, and comorbidities and these factors were insufficiently considered in the APACHE II mortality predictors. Again, no toxicity from statins was reported.

# 1.5. Potential Mechanisms of Action of Statins in Sepsis

Statins are a class of lipid-modifying drugs which inhibit the HMG-CoA reductase. This enzyme catalyzes the conversion of hydroxymethylglutaryl-CoA to mevalonate, an early rate limiting step in cholesterol synthesis. Over the past decade, statins have been identified as potential immune modulators. The mechanisms of immune modulation are complex and are regarded as lipid independent as they are not related to lowering of LDL cholesterol. However, most of the immunomodulatory effects of statins are due to inhibition of HMG-CoA reductase and the subsequent downstream effects of inhibition of isoprenoid lipid production. This leads to alterations in G-protein mediated signaling, alterations in adhesion molecules, and cell proliferation. Most of these immunomodulatory effects can be reversed by mevalonate supplementation supporting the conclusion that HMG-CoA inhibition is the main immunomodulatory pathway by which statins act. However, non-HMG-CoA mediated anti-inflammatory effects have been reported. For example, statins bind directly to leukocyte CD11a/CD18 and thus interfere directly with leukocyte binding to ICAM-1. The cellular functions affected by inhibition of HMG-CoA reductase are ubiquitous and involve neutrophil, monocyte, lymphocyte, epithelial and endothelial cell biology.

Statins affect the production of many cytokines including IL-6, IL-8, TNF-a, monocyte chemotactic protein-1 (MCP-1), and CRP. Statins alter neutrophil attachment to the endothelium by directly interfering with adhesion as noted above but also by down-regulating surface expression of P-selectin, CD11b, and CD18. Statins also inhibit lymphocyte function antigen-1 mediated neutrophil adhesion, inhibit LPS induced expression of monocyte toll-like receptor 2 and 4, improve platelet function, inhibit fibrinolysis, and increase endothelial nitric oxide synthase activity. Many of the inflammatory pathways modulated by statins are thought to involved in the pathogenesis of sepsis and ALI.

#### 1.6. Animal and Human Studies of Statins in Experimental Sepsis

Several animal models of sepsis demonstrate that statin pretreatment improves survival, biomarkers of inflammation, and cardiac function (Tabulated in Appendix C). One study by Merx et al. demonstrated that treatment of mice with statins 6 and 18 hours *after* CLP improved cardiac function and survival time (23 vs. 37 hours; p<0.05). This effect was seen with multiple statins, suggesting a class effect. Pretreatment with simvastatin 18 hours before CLP improved cardiac function and hemodynamic status within 20 hours of CLP and extended survival from 28 to 108 hours. Yasuda et al. demonstrated that pretreatment for 3 days with oral simvastatin increased survival three days post CLP from 26% to 73% and at post-op day 2 from 42% to 84%.

Short term statin treatment attenuated acute lung injury in a model using intestinal ischemiareperfusion. Reductions in both blood and BAL concentrations of IL-1, II-6, and IFN- $\alpha$  and pselectin were reported. Reduced lung wet/dry ratios and histological lung injury scores were also observed.

Randomized controlled studies and observational studies in sepsis and ALI demonstrate that statins can reduce inflammation in acute disorders over a period of days. Steiner et al. administered LPS intravenously after four doses of simvastatin 80 mg/day vs. placebo in healthy subjects and found blunted responses of monocyte tissue factor expression and CRP at 4 and 8 hours post infusion. Niessner et al. pretreated human volunteers with high dose statins or placebo prior to administering intravenous lipopolysaccharide (LPS). A resultant inhibition of toll-like receptor 4 and 2 led to reduced plasma levels of TNF $\alpha$  and MCP-1 as early as 4 hours after LPS injection. In a randomized controlled trial in healthy volunteers, pretreatment with 4 days of simvastatin attenuated bronchoalveolar lavage levels of IL-1 $\beta$ , TNF $\alpha$ , myeloperoxidase,  $\alpha$ -1 antitrypsin, and matrix metalloproteinases-7,8,9 six hours after IV LPS. Plasma CRP was also reduced.

In additional human studies, discontinuation of statins upon hospital admission was associated with worse outcomes. In patients with sepsis, Kruger et al. noted increased mortality in patients in whom statins had been stopped. In a RCT of aspirin plus heparin versus aspirin plus tirofiban, Heeschen et al. noted that patients in whom statins were discontinued had higher combined non-fatal myocardial infarction and death rates than non-statin users. Both groups had higher rates than those continued on statins. These associations were observed as early as 72 hours following randomization. Spencer et al. demonstrated that statin removal resulted in higher in-hospital morbidity and mortality in patients presenting with acute coronary syndrome. Patients in whom statins were initiated at the time of the acute coronary syndrome also fared better than patients who never received statins. Two studies in surgical patients demonstrate worse outcomes when statin therapy was not restarted immediately post-operatively. Collard et al. reported higher mortality following coronary bypass surgery if statins were not restarted (OR 2.64 (95% CI: 1.32-5.26). Le Manach et al. reported that myocardial necrosis in vascular surgery patients was greater in patients when statin therapy was not restarted until post-operative day 4 (OR 2.9. CI: 1.6-5.5). Schouten reported in 298 patients undergoing major vascular surgery missing statin doses for a median of 3 days post-operatively (70 patients) had a hazard ration of 4.6 (95% CI 2.2-9.6) for troponin leak and a hazard ration for a 30 day outcome combined variable of death, myocardial infarction or death of 7.5 (95% CI 2.8-20.1).

In summary, acute and chronic immunomodulatory effects of statins are potentially useful for the prevention and treatment of sepsis. While the bulk of observational human and animal studies examine pretreatment with statins, two small RCTs in normal humans suggest the onset of the beneficial effects for the treatment of sepsis may be brief. Finally, one animal study demonstrated benefit after experimental sepsis and two small RCTs showed promising results with acute administration of statins for patients presenting with sepsis.

#### 1.7. Rationale for Selecting Rosuvastatin

The pleiotropic effect of statins appears to be a class effect. As outlined above and in Appendix C, the retrospective and prospective human studies have included multiple statins. Animal experiments show consistent effects regardless of choice of statin. However, in the context of human trials of the FDA approved statins, rosuvastatin has the best drug-drug interaction profile. This attribute not only will likely improve the safety of this agent but also reduced the number of exclusions we will need in order to avoid drug-drug interactions. Rosuvastatin is 10% less protein bound than atorvastatin or simvastatin and is 10-15% more bioavailable. It is hydrophilic as opposed to the latter two lipophilic drugs. Its side effect profile is comparable to other statins (Appendix C). Less than 0.1% of patients receiving rosuvastatin developed a 10 fold increase in CK. Significant hepatic dysfunction or failure has not been reported in the observational trials to date. Preliminary data from an ALI study of 60 patients randomized to simvastatin 80 mg/day vs. placebo revealed no differences in AST, ALT or CK values between populations. Furthermore, the frequency of adverse events, serious adverse events and drug related adverse events were not different (personal communication, [name]).

### 1.8. Rosuvastatin Pharmacokinetics and Dose Selection

Rosuvastatin is rapidly absorbed with peak levels at 3-5 hours post dosing with a half life of 10-20 hours. Concomitant use of food reduces the rate of absorption by 20% but does not impact AUC. Time of day of dosing has no impact. Antacids should be administered 6 hours before or after rosuvastatin to avoid impact. Eighty-eight percent of this drug is bound by plasma proteins, mostly albumin. Only 10% of rosuvastatin is metabolized. It is primarily excreted in stool (90%). It is not cleared through a renal mechanism. However caution is noted in renal failure, as risk for rhabdomyolysis may be increased in this setting. Dosing should be reduced in renal failure for patients not receiving chronic renal replacement therapy.

Since the anti-inflammatory effect of statins appears to be a class effect we have chosen rosuvastatin because it appears to be safe and has the fewest drug interactions of the statins. It also has a 10-20 hour half life allowing for once per day dosing.

We have chosen a moderate dose of rosuvastatin (20 mg maintenance dose, with adjustments for Asian decent and renal failure not compensated by renal replacement therapy). However, given the uncertainty of absorption, hepatic uptake and elimination we will assess drug levels after 60 patients are enrolled and adjust dosing if necessary (see section 5.2).

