# DEFINITIONS

Acute Kidney Injury: Acute kidney injury network Stage 3 disease, defined as a threefold increase in creatinine from baseline or the need for dialysis

**Asian:** A person having origins in any of the original peoples of the Far East, Southeast Asia, or the Indian subcontinent including, for example, Cambodia, China, India, Japan, Korea, Malaysia, Pakistan, the Philippine Islands, Thailand, and Vietnam.

**Completing 48 hours of UAB (from weaning form)**: Defined as the date (calendar day) that the subject reaches exactly 48 hours of UAB. Example: if subject meets UAB at 1900 on 6/1/06 and does not return to AB, then the date of completing 48 hours of UAB would be 6/3/06.

**Date of first UAB (from Study Termination form)**: Defined as the first day that the subject is on UAB from midnight to midnight. Example: if subject meets UAB at 1900 on 6/1/06, then the date of first UAB would be 6/2/06, as long as subject does not return to AB on 6/2/06. **Extubation**: Removal of an orotracheal, nasotracheal tube, or unassisted breathing with a tracheostomy

**Home**: level of residence or health care facility where the patient was residing prior to hospital admission

**Hospital Mortality to Day 60:** This primary endpoint includes all deaths following randomization in any heath care facility prior to discharge "home" until study day 60. Study subjects still in a health care facility at study day 61 are considered alive for this endpoint.

**NYHA**: New York Heart Association Class IV subjects (defined as subjects who have cardiac disease resulting in inability to carry out physical activity without discomfort. Symptoms of cardiac insufficiency or an anginal syndrome may be present even at rest. If any physical activity is undertaken, discomfort is increased).

**Sepsis:** SIRS criteria plus suspected or known infection. Since intubation and hypoxemia is a requirement for enrollment into this trial, participants will, by definition, meet the respiratory SIRS criterion. They must also meet two of three non-respiratory SIRS criteria.

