# 5.1. Statin or Placebo Administration

Rosuvastatin or placebo will be administered through an enteral feeding tube or administered orally following extubation when patients are able to safely take oral medications. The type and placement of the enteral feeding tube (nasogastric, nasoenteric, PEG, orogastric, oroenteric, etc.) and the ability to safely take oral medications will be determined by the patient's primary team. Study drug will be blinded with an identical appearing placebo.

The first study drug dose (rosuvastatin or placebo) will be administered within 4 hours of randomization as a loading dose of 40 mg.

- 1. Subsequent doses will be at 10 am daily (+/- 4 hours) starting on the next calendar day as a maintenance dose of 20 mg.
- 2. If for any reason a maintenance dose is not administered at the intended time, it may be administered subsequently but not more than 12 hours after the intended time of administration.

Should the time be > 12 hours since last scheduled dose, the patient will not receive a dose on that study day but will be given a loading dose on the next calendar day. Maintenance dosing will continue on subsequent days.

Daily doses will be reduced by 50% for patients with a creatinine level greater than or equal to 2.8 mg/dL who are not on renal replacement therapy. Loading doses will not be reduced.

Daily dosing:

- Each subject will receive full dose if last known creatinine value less than 2.8 mg/dL.
- Each subject will receive half dose if last known creatinine value greater than or equal to 2.8 mg/dL (unless receiving renal replacement therapy in which case a full dose will be given).

If used, antacids should be administered no closer than 6 hours before or after administering rosuvastatin to avoid affecting absorption of study drug. The dosage need not be adjusted for ketoconazole, erythromycin, itraconazole, fluconazole, warfarin or digoxin.

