# 9.3. Minimization of Risks

Federal regulations at 45 CFR 46.111(a) (1) requires that risks to subjects are minimized by using procedures which are consistent with sound research design. There are several elements of study design in the present protocol that meets this human subject protection requirement.

First, several of the exclusion criteria prohibit participation of patients who might be at increased risk from the effects statins. For example, patients who have intolerances or allergies to statins, active hypothyroidism, and who are taking medications that may unfavorably interact with

statins are excluded. Furthermore, patients with rhabdomyolysis or hepatic injury are excluded as the detection of statin toxicity may be more difficult in such individuals. While these are considered relative contraindications in clinical care, for this trial they will be absolute contraindications.

Second, patients with ALI and ARDS may also have underlying conditions that would benefit from statins as part of usual clinical care, such as ischemic heart disease or hyperlipidemia. We will exclude patients if their attending physician plans to administer statins during the course of ALI for these or any other usual care indications.

Third, there are provisions in the protocol for reduction of the study drug dose for low creatinine clearance by reducing the dose when the serum creatinine is 2.8 mg/dl or greater and for anticipated genetic differences in hepatic drug clearance.

Fourth, levels in the first 60 patients will be evaluated by both the Steering Committee and the DSMB to assure that the achieved levels approximate the targeted range. The Steering Committee recommendation to either maintain or change the study drug dose will be reviewed by the DSMB during the protocol-specified 100 patient safety evaluation.

Finally, we will monitor for adverse effects to liver and muscle by monitoring CK and ALT. We will stop study medications if CK rises to more than 10 times ULN or ALT rises to more than 8 times ULN. Myopathy will be recorded in the case report forms, but study drug will not be stopped unless CK is 10 times ULN.

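### Sections 1.8 and 9.3 announce a dose adjustment for Asian descent or genetic differences in clearance that the operative dosing rules do not contain

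*Protocol*

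**What the plan says.** Two descriptive sections announce patient-level dose adjustments. Section 1.8 gives the regimen as a "20 mg maintenance dose, with adjustments for Asian decent and renal failure not compensated by renal replacement therapy" (the spelling is the protocol's). Section 9.3 opens by noting that "Federal regulations at 45 CFR 46.111(a) (1) requires that risks to subjects are minimized" and sets out five design elements offered as meeting that requirement. In the third it states that "there are provisions in the protocol for reduction of the study drug dose for low creatinine clearance", which it ties to a serum creatinine of 2.8 mg/dl or greater, "and for anticipated genetic differences in hepatic drug clearance".

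The rules that govern administration are in the Study Summary (Study Drug Dosing) and Section 5.1, and these two agree with each other. Section 5.1 says: "Daily doses will be reduced by 50% for patients with a creatinine level greater than or equal to 2.8 mg/dL", limited to patients not on renal replacement therapy, and leaves loading doses unreduced. It then says: "Each subject will receive full dose if last known creatinine value less than 2.8 mg/dL".

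The Definitions describe Asian as "A person having origins in any of the original peoples of the Far East, Southeast Asia, or the Indian subcontinent", followed by a list of example countries.

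**The concern.** The protocol says twice that it adjusts the dose for a patient characteristic other than renal function: once as descent (1.8) and once as genetic differences in hepatic clearance (9.3). The sections a site uses to dose a patient do not mention either. Section 9.3 is more than background. It states as fact that the provision exists, in a list meant to show that a human-subject protection rule is met. Section 10 requires IRB approval before any subject is entered, so a reviewing board would read 9.3 as describing the trial as it will be run.

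Two things are at stake. The first is whether the safety statement is accurate, because a described protection is not delivered. The second is whether the dosing instruction is clear, because a reader of 1.8 and a reader of 5.1 would form different views of how the same patient is dosed.

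**Working it through.** The protocol gives no figure to reproduce on this point. The check sets the passages side by side and asks whether any other part of the document supplies the missing rule.

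1. **Adjustments announced.** Section 1.8: Asian descent, and renal failure without renal replacement therapy. Section 9.3: creatinine of 2.8 mg/dl or greater, and genetic differences in hepatic clearance. That makes two kinds, one renal and one based on ancestry or genotype.

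2. **Adjustments implemented.** The Summary and Section 5.1 contain one kind, renal.

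3. **Is 5.1 only silent?** No. Its daily dosing rule covers every patient: creatinine below 2.8 mg/dL, full dose; 2.8 mg/dL or above, half dose, unless on renal replacement therapy, then full dose. These branches are exhaustive and leave no place for a further reduction. Section 5.1 therefore conflicts with 1.8 and 9.3.

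4. **Does another section supply the rule?**
   - The plasma-level review (Summary, Drug level specimens) acts on mean levels in about 30 rosuvastatin patients and could change the dose for the whole trial. It is not an individual adjustment. Section 9.3 lists it as the fourth measure, separate from the genetic provision in the third.
   - The exclusion criteria (4.3) and the rules for premature withdrawal (5.4) do not mention ancestry or genotype.
   - Appendix H banks DNA for future studies that are not yet defined. Nothing links genotype to dosing.
   - Asian is defined, but no dosing, eligibility or withdrawal rule uses the term.

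   The dosing text in the Summary and 5.1 reads as complete, so redaction or a broken table does not explain the gap.

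5. **How many patients could such a rule cover?** The protocol does not give the share meeting the definition. Assuming 2% to 10% of the maximum enrollment:
   - 0.02 × 1000 = 20 and 0.10 × 1000 = 100 patients;
   - about half on rosuvastatin: 10 to 50;
   - among the approximately 30 rosuvastatin patients in the plasma-level check: 0.02 × 30 = 0.6 to 0.10 × 30 = 3.

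   These count patients whom a rule would cover. They do not count patients dosed contrary to Section 5.1.

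6. **Effect on the comparison.** Placebo is identical in appearance (5.1), and randomization is stratified by institution and by shock (4.6). A site that made its own adjustment for ancestry would do so without knowing the arm. Exposure in the active arm could then vary or be diluted, but the practice would not differ systematically between arms.

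**The case against.** The strongest reply is that sites dose from Section 5.1, that 5.1 and the Summary agree, and that 1.8 is background with no amount, threshold or timing for a site to act on. On this view dosing will be uniform and the fault is a stray phrase. Most of this stands. Uniform dosing under 5.1 is the likelier outcome, and divergence between sites is only a possibility. But if dosing is uniform under 5.1, then Section 9.3 is untrue as written, because it asserts a provision the protocol lacks.

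A second reply is that the definition of Asian may serve the race subgroup listed in Section 7.2. It may, although no other racial category is defined. That would account for the definition but not for the statements in 1.8 and 9.3.

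A reader might infer three stronger things, and the documents support none of them:

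- **That mixed practice would confound the CK, ALT and AST safety comparison or the plasma-level check.** Blinding and stratification by institution rule out the first. For the second, the assumed share implies about 0.6 to 3 of some 30 patients, and they would matter only if their sites departed from 5.1.
- **That the risk-benefit case depends on this adjustment.** Section 9.5 does not mention dose adjustment; it argues from observational, animal and small-trial data. The clause is half of one of five items in 9.3. The exclusions, the drug-level review and the CK and ALT monitoring do not depend on it.
- **That the DSMB relied on it.** Its dose review, as described in the Summary, uses unblinded drug levels, adverse events, clinical and laboratory findings, and outcomes.

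**Conclusion.** The contradiction is real. The protocol announces two kinds of patient-level dose adjustment and implements one. The adjustment for Asian descent or genetic differences in clearance appears in 1.8 and 9.3 but in neither set of dosing rules, and following the dosing section exactly leaves a stated risk-minimization measure undelivered.

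This is an internal inconsistency in a safety provision. It does not threaten the validity of the randomized comparison; the most that could follow statistically is some variation in exposure within the active arm, and only if sites improvised. The 20 to 100 patients whom such a rule might cover rest entirely on the assumed 2% to 10% share. The contradiction itself rests on no assumption.

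The document does not show why the mismatch arose, and nothing here implies which dosing rule is right.

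**What to change.** Reconcile the Definitions, the Study Summary and Sections 1.8, 5.1 and 9.3 so that all state the same rule. The sponsor's clinical team should decide which.

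- **If the statements in 1.8 and 9.3 are withdrawn:** delete them, inform the IRBs and the DSMB, and keep the definition of Asian only if it serves another purpose, such as the race subgroup.
- **If a rule is retained:** state it in full in the Summary and Section 5.1, align 1.8 and 9.3 with it (they now name different criteria, descent and genetic differences), and have it applied identically in both blinded arms.

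The first option costs a wording amendment and a notice to the reviewing bodies. The second costs the amendment and, if the rule is applied through the randomization or dispensing system, one added field. Neither changes the sample size, the endpoints or the analysis.
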